#### 7.5.2.4 Gadolinium

There are known adverse events after the use of Gadolinium as contrast material in MRI scans. Caution must be taken with patients with current and previous renal failure.

## 7.5.3 Physical examination, weight, height

Physical examinations will be performed and weight will be measured on all visits. This may be performed by the Investigator or any other qualified healthcare professional. The information on physical examinations must be present in the source-documentation at the study site. Height will be registered only during the screening / baseline period. Significant

findings present before the start of the study treatment must be included in the Relevant Medical History / Current Medical Conditions Case Report Form. Significant findings after the start of the study drug meeting the definition of an AE must be recorded in the Adverse Event Case Report Form (eCRF).

## 7.5.4 Vital signs

Body temperature, blood pressure in supine position, and heart rate in supine position will be evaluated on all main phase visits and on Visits 13 (week 36), 16 (week 48), 19 (week 60), 22 (week 72), 25 (week 84), 28 (week 96), and 29 (week 100) in the extension phase.

#### 7.5.5 Performance status

Eastern Cooperative Oncology Group (ECOG) performance status will be evaluated on each visit in the main phases and on Visits 13 (week 36), 16 (week 48), 19 (week 60), 22 (week 72), 25 (week 84), 28 (week 96), and 29 (week 100) in the extension phase, using the criteria on Table 7-3.

Table 7-3 Eastern Cooperative Oncology Group (ECOG) performance status scale

Grade	ECOG
0	Fully active, able to carry out all pre-disease activities without restriction
1	Restricted in physically strenuous activity, but ambulatory and able to carry out work of a light or sedentary nature, e.g., light housework, office work.
2	Ambulatory and capable of all self-care but unable to carry out any work activities. Up and awake for approximately more than 50% of time.
3	Capable of only limited self-care, confined to bed or chair more than 50% of waking hours.
4	Completely disabled. Unable to carry out any self-care. Completely confined to bed or chair.
5	Deceased

# 7.5.6 Laboratory evaluations

Laboratory samples will be submitted to a local laboratory for analysis, except alpha subunit which will be submitted to a central laboratory. Patients will fast overnight for 12 hours before all blood samples are collected. Blood samples must be performed in the morning. Drinking water is allowed during this period.

Details about the central laboratory, including collection and submission of samples, report of results, and warning procedures for extreme values, will be provided in the Investigator's Binder.

## 7.5.6.1 Hematology

Hematology parameters will be evaluated in the Screening Period, before administration of the study drug, and on every Main Phase visit (except Visit 2, Visit 3 [Week 3], Visit 6 [Week 11], and Visit 10 [Week 24]), and will include: WBC count with differential, hemoglobin, HCT, RBC count and platelet count, and differential.

#### 7.5.6.2 Coagulation

Coagulation parameters APTT and PT will be evaluated on visit 1 (screening), visit 2 (baseline), visit 6, and visit 10 (completion of the study) for all patients. Coagulation parameter PT will also be evaluated on visit 3, visit 4, visit 401 (after 48 days), and visit 5 for patients randomized to the double-blind treatment arm of pasireotide LAR. Coagulation parameters will be collected before administration of the study drug.

During the Extension Phase, evaluations will be performed first on visit 10 (Week 24), and then every 6 months thereafter (i.e., Weeks 48, 72, and 96).

#### 7.5.6.3 Chemistry

A complete chemistry profile will be evaluated in the screening period and before administration of the study drug on each visit (except on Visit 2, Visit 3, Visit 6, and Visit 11, the Follow-up Visit) and will include: total cholesterol, low density lipoprotein (LDL) cholesterol, high density lipoprotein (HDL) cholesterol, triglycerides, calcium, phosphorus, chloride, sodium, potassium, inorganic phosphorus, creatinine, urea, uric acid, CPK, LDH, alkaline phosphatase,  $\gamma$ -GT, total protein, albumin, SGOT, SGPT, total bilirubin. In the Extension Phase, the chemistry profiles will be evaluated on visit 10 (Week 24) and then every 6 months thereafter (Weeks 48, 72, and 96).

[figure not shown]
If total bilirubin concentration increases more than 2.0 times the upper limit of normal, total bilirubin must be differentiated in direct and indirect reagent bilirubin on all visits.

Fasting blood glucose, insulin, and fasting chemistry evaluations will be performed in the screening phase and before administration of the study drug on each visit, except on Visit 2, Visit 3 (Week 3), Visit 6 (Week 11), and Visit 11 (Week 28, Follow-up Visit) in the Main Phase; they will also be performed on Weeks 48, 72, and 96 in the Extension Phase.

Liver function tests (ALT, AST, total bilirubin, albumin, ALP, and  $\gamma$ -GT) will be evaluated on visit 1 (screening), visit 2 (baseline), visit 6, and visit 10 for all patients. Liver function tests will also be evaluated on visit 3, visit 4, visit 401 (after 48 days), and visit 5.

HbA1c evaluations will be performed in the screening period (these will be considered as baseline data), on Weeks 12 and 24 in the Main Phase, and on weeks 48, 72, and 96 in the Extension Phase.

Vitamin B12 and folic acid evaluations will be performed in the Screening Period (these will be considered as baseline data), on Week 24 in the Main Phase, and on weeks 48 and 96 in the Extension Phase.

## 7.5.6.5 Serology

Hepatitis B surface antigen (HBs-Ag) and Hepatitis C antibody (anti-HCV) tests will be performed on visit 1 (screening).

## 7.5.6.6 Urinalysis

Specific gravity, pH, glucose, protein, bilirubin, ketones, leukocytes, and blood will be evaluated. Urine must be collected in the Screening Phase and before administration of the study drug on each visit (except on Visit 2, Visit 3, Visit 6, and Visit 11 or Follow-up Visit) in the Main Phase and on Weeks 48, 72, and 96 in the Extension Phase.

#### 7.5.6.7 Pregnancy test

Blood pregnancy test is performed in the screening period, on Weeks 12 and 24 in the Main Phase, and on Weeks 48, 72, and 96 in the Extension Phase. It may be performed on the Follow-up Visit ( $56 \pm 3$  days after the last dose of the study medication) if the patient reports late menstruation or at the physician's discretion. Patients considered post-menopausal (defined as 12 months of natural (spontaneous) amenorrhea or 6 months of spontaneous amenorrhea with FSH blood levels > 40 mIU/mL before or during the study) are not required to performed subsequent pregnancy tests.

The study drug treatment must be withdrawn in case of pregnancy.

In order to ensure patient safety, every pregnancy in a patient under study drug administration must be reported to Novartis within 24 hours after acknowledgement. Pregnancy must be followed to determine the outcome, including miscarriage or abortion, details about the birth and presence or absence of any birth defects, congenital anomalies or maternal and/or newborn complications.

For information on pregnancy reports, refer to section 8.2.

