Hypopituitarism may occur in pituitary macroadenomas as a result of (a) compression of the pituitary stalk, leading to a decrease of hypothalamic hormones reaching the pituitary gland; (b) compression of the normal pituitary tissue; and (3) hypothalamic involvement of the pituitary tumor (Dekkers et al 2008). The hypogonadism seen with these adenomas is frequently associated to the increase in blood prolactin levels (usually < 200 ng/mL) (Jaffe 2006). Patients with hypopituitarism are at increased risk of mortality due to cardiovascular, cerebrovascular, and/or respiratory disease (Bates et al. 1996)(Rosen et al. 1990)(Bulow et al 1997)(Nilsson et al 2000)(Tomlinson et al 2001).

Hypopituitarism due to NFPA may produce different symptoms. Four out of five patients with NFPA experience secondary hypothyroidism, and 3 out of 5 experience secondary adrenal failure (Jaffe 2006). Most patients also experience signs and symptoms of hypogonadism, frequently as a result of direct compression by a large adenoma and growth hormone (GH) deficiency (Jaffe 2006). Approximately 60% to 80% of patients experience visual field defects, a consequence of tumor pressure on the optic chiasm (Jaffe 2006)(Dekkers et al 2007). In some cases, these tumors compress other surrounding brain tissues and lead to dysfunctions in the cranial nerves (Jaffe 2006)(Vance 2008). Frequently, patients experience headache, although this event is not diagnosed (Vance 2008).

The evaluation of the tumor volume and location of the pituitary adenoma are performed more efficiently by magnetic resonance imaging (MRI) (Dekkers et al 2008). Screening hormone tests that may determine pituitary deficiency include ACTH, cortisol, TSH, free thyroxin (T4), insulin-like growth factor I (IGF-1), luteinizing hormone (LH), follicle-stimulating hormone (FSH), and testosterone (in men) (Vance 2008). Prolactin is also useful for diagnosis, but it must be diluted if the patient presents a large lesion, in order to avoid the "hook effect" and a possible mistaken diagnosis (Vance 2008) (the hook effect may be defined as falsely low values in an immunoassay when an extremely large amount of antigens affects the binding ability of the antibody added).

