Merola et al 1993	19	0.15 - 0.3 mg/day SC	1-12	Decreased: 5% Unchanged: 95%	9 evaluable patients Improved: 11% Unchanged: 89%
Gasperi et al 1993	8	0.3 mg/day SC	3-6	Decreased: 0% Unchanged: 75% Increased: 25%	5 evaluable patients Improved: 20% Unchanged: 60% Worsened: 20%
de Bruin et al 1992	4	1.2 mg/day SC	3-6	Unchanged: 100%	Improved: 75% Unchanged: 25%

Combination therapy with dopamine receptor agonist cabergoline and somatostatin analogue octreotide in 10 patients with NFPA produced similar results (Andersen et al 2001). Tumor volume decreased in 6 patients (60%), remained unchanged in 3 (30%), and increased in 1 (10%) patient. Visual acuity improved in 3 (30%) patients and remained unchanged in the other 7 (70%) patients.

A clinical therapy able to control tumor growth and possibly capable of decreasing tumor size would be highly advantageous to patients with NFPA. These therapies could be used presurgically to improve surgical result, leading to few patients with remaining tumors, or to control tumor growth or recurrence after surgery, thus avoiding the need for radiation therapy. Another possible benefit related to tumor decrease would be the receovery from hypopituitarism.

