# 3.2 Secondary objectives

- To evaluate the effect of pasireotide LAR in mean tumor volume variation between baseline and treatment weeks 4, 12, 24, 48, 72, and 96.
- To evaluate the effect of pasireotide LAR in mean percent tumor volume variation between baseline and treatment weeks 4, 12, 24, 48, 72, and 96.
- To evaluate the effect of pasireotide LAR in the proportion of patients reaching tumor volume decrease of at least  $\geq 20\%$  after 4, 12, 48, 72, and 96 weeks of treatment.
- To evaluate the effect of pasireotide LAR on time to tumor response.
- To evaluate the effect of pasireotide LAR on the disease-related symptoms \*
   \* Disease-related symptoms to be evaluated: headache, visual disorders, fatigue, decreased libido, erectile dysfunction (for men only), menstrual irregulative or interruption (only for non-menopausal women).
- To evaluate the effect of pasireotide LAR on the pituitary function on weeks 4, 12, 24, 48, 72, and 96.
- To evaluate the effect of pasireotide LAR on the alpha subunit levels on weeks 4, 12, 24, 48, 72, and 96.
- To evaluate the overall safety and tolerability of pasireotide LAR.
- For the extension phase: duration of response for patients considered as responders (i.e., patients reaching a tumor volume decrease of at least 20% compared to the initial tumor volume).
- To evaluate the percentage of patients remaining with stable tumor volume during the study.

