#### 5.2 Exclusion criteria

- 1. Patients requiring surgical intervention for relief of any sign or symptom related to tumor compression.
- 2. Previous pituitary surgery.
- 3. Previous medical treatment for pituitary tumor.
- 4. Patients who received pituitary radiation within 10 years before the enrollment visit (Visit 2).
- 5. Prolactin (PRL) levels > 100 ng/mL. (PRL evaluation must be performed with diluted samples in order to ensure prevention of the "hook effect").
- 6. Patients with optic chiasm compression, causing clinically significant acute visual field defects.
- 7. Diabetic patients whose blood glucose is poorly controlled, as proven by HbA1C > 8%. Patients with known history of fasting glucose impairment or diabetes mellitus with HbA1c < 8% may be enrolled; however, blood glucose and antidiabetic treatment must be closely monitored throughout the study and adjusted as required.
- 8. Patients with known gallbladder or bile duct disease, or acute or chronic pancreatitis (patients with asymptomatic colelithiasis and asymptomatic dilation of the bile duct may be enrolled).
- 9. Patients with abnormal coagulation (increased PT or APTT 30% above normal limits) or patients who have received antiacoagulants that affect PT (prothrombin time) or APTT (activated partial thromboplastin time).
- 10. Patients with congestive heart failure (NYHA Class III or IV), unstable angina, persistent ventricular tachycardia, ventricular fibrillation, advanced cardiac block, or history of acute myocardial infarction within 24 weeks before the enrollment visit (Visit 2).
- 11. Screening (Visit 1) or baseline (pre-dose, Visit 2) QTcF > 450 msec.
- 12. Patients with history of syncope or family history of idiopathic sudden death.

- 13. Patients with persistent or clinically significant cardiac arrhythmias.
- 14. Patients with Torsades de Pointes risk factors, such as uncorrected hypocalemia, uncorrected hypomagnesemia, heart failure, clinically significant / symptomatic bradycardia, or high degree AV block.
- 15. Patients with concurrent disease(s) that might prolong the QT interval, such as autonomous neuropathy (caused by diabetes or Parkinson's disease), HIV, cirrhosis, uncontrolled hypothyroidism, or heart failure.
- 16. Patients on medication(s) known to prolong the QT interval.

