- 17. Patients with liver disease or history of liver disease, such as cirrhosis, active chronic hepatitis B and C, or persistent chronic hepatitis, or patients with ALT and/or AST > 2 x ULN, total blood bilirubin > 1.5 x ULN, and serum albumin < 0.67 x LLN.
- 18. Patients with blood creatinine > 2.0 x ULN.
- 19. Patients with WBC  $< 3 \times 10^9 / L$ ; Hgb < 90% LLN; PLT  $< 100 \times 10^9 / L$ .
- 20. Patients with any current or previous medical condition that, in the investigator's opinion, might interfere in the study conduction or evaluation of the study results.
- 21. Patients with history of immunological impairment, including positive result for HIV tests (ELISA and Western blot). HIV tests will not be required; however, previous medical history will be analyzed.
- 22. Patients with known hypersensitivity to somatostatin analogues or any other pasireotide LAR compound.
- 23. Patients with active malignant disease within the last five years (except for basal cell carcinoma or in situ cervix carcinoma).
- 24. Patients with presence of uncontrolled, acute suspected, or active chronic infection.
- 25. Pregnant or breastfeeding patients, or patients of childbearing potential who do not adopt a clinically acceptable contraceptive method. If a woman is participating in the study, then one contraceptive method will be sufficient (pill or diaphragm), and the partner must use condoms. If an oral contraceptive is used in addition to condoms, the patient must have adopted this method at least two months prior to enrollment in the study, and must agree to continue to use it throughout the study, and for three months after the end of the study. Sexually active male patients are required to use condoms during the study and for three months after the end of the study, as a precautionary measure (the available data do not suggest any increase in reproductive risk with the study drugs).
- 26. Study participants on the investigational drug 30 days prior to the enrollment visit (Visit 2). Patients must have recovered from all side effects from other investigational therapies.

- 27. Patients with history of non-compliance to medical regimens, or patients considered potentially unsafe, or any circumstance at the time of study enrollment that might prevent the completion of the entire study or the follow-up required.
- 28. Patients with history or recurrence of undue use / abuse of alcohol or drugs within 12 months previous to visit 1 (screening).

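### Protocol 7.5.6.7 ends pregnancy testing after 12 months of spontaneous amenorrhea with no FSH, age or cause condition, in a disease that can itself stop menses

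*Protocol*

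**What the plan says.** Protocol 7.5.6.7 schedules a blood pregnancy test at screening and at Weeks 12, 24, 48, 72 and 96. It then exempts patients considered post-menopausal, "defined as 12 months of natural (spontaneous) amenorrhea or 6 months of spontaneous amenorrhea with FSH blood levels > 40 mIU/mL". The sentence ends: "before or during the study) are not required to performed subsequent pregnancy tests". A further test at the Follow-up Visit is optional, prompted by a reported late period or by the physician's judgement. The section gives no step for restarting tests, and it requires the drug to be withdrawn if pregnancy occurs.

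Other sections bear on this:

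- Section 3.2 lists among disease-related symptoms "menstrual irregulative or interruption (only for non-menopausal women").
- Section 1.1 says of the disease in general: "Most patients also experience signs and symptoms of hypogonadism". It adds: "The hypogonadism seen with these adenomas is frequently associated to the increase in blood prolactin levels".
- Section 1.1 also says: "Another possible benefit related to tumor decrease would be the receovery from hypopituitarism".
- Exclusion 32 removes confirmed hypogonadism unless it is treated with stable replacement. It exempts menopause only where it is physiological.
- Exclusion 25 excludes "patients of childbearing potential who do not adopt a clinically acceptable contraceptive method". Section 11.4 repeats the contraceptive requirement and says the fetal risk is unknown.

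**The concern.** The two routes to post-menopausal status are not equally safe in this population. The 6-month route carries a hormonal check. The 12-month route relies on duration and on the amenorrhea being spontaneous, and amenorrhea caused by the adenoma is spontaneous too. Exclusion 32 separates physiological menopause from hypogonadism, but 7.5.6.7 does not carry that distinction over.

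The plan also expects menses to return in some women. Footnote c of SAP Table 10 counts a change from no regular menses at Visit 1 to regular menses later as an improvement. A woman misclassified as post-menopausal could regain fertility on treatment after her required tests have ended. The optional Follow-up Visit test helps her little, because a late period cannot be noticed by someone who is not menstruating. That leaves the physician's discretion.

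**Working it through.** The plan gives no figure of its own here, so there is nothing to reproduce. The check has three parts.

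**1. Who can be misclassified.** Reading 7.5.6.7 against the eligibility criteria:

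- Women with confirmed, untreated hypogonadism do not enter (exclusion 32). Estradiol, LH, FSH and prolactin are measured at screening.
- Women on stable replacement do enter under exclusion 32.
- Women whose hypogonadism was present but not confirmed at screening also enter.
- Women who reach 12 months of amenorrhea on study are added only if the timing phrase in 7.5.6.7, which covers the period before or during the study, governs both routes. It may attach only to the FSH route.

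The documents give no count for any of these groups. Total enrolment is 23, men and women together.

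**2. Tests and doses at stake.** Inputs:

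- Post-screening tests fall at Weeks 12, 24, 48, 72 and 96 (7.5.6.7).
- The injection given at Week 12 is number 4, at Week 24 number 7, at Week 48 number 13 and at Week 72 number 19. The last is number 24 at Week 92 (Tables 7-1 and 7-2).
- Blood is drawn before dosing (Table 7-1 footnote 6, Table 7-2 footnote 2).

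Take 12 months as 52 weeks, and let t be the onset of amenorrhea in weeks from Day 0. The test at Week W is waived when t + 52 ≤ W. A waived pre-dose test can affect only doses from that visit onward, so if the injection at the first waived visit is number k, the count is 24 − k + 1. At Week 96 no dose remains.

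| First waived test | Onset t (weeks) | Tests waived | Doses a waived test could have stopped |
|---|---|---|---|
| Week 12 | t ≤ −40 | 5 | 24 − 4 + 1 = 21 |
| Week 24 | −40 < t ≤ −28 | 4 | 24 − 7 + 1 = 18 |
| Week 48 | −28 < t ≤ −4 | 3 | 24 − 13 + 1 = 12 |
| Week 72 | −4 < t ≤ 20 | 2 | 24 − 19 + 1 = 6 |
| Week 96 | 20 < t ≤ 44 | 1 | 0 |

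These are maxima. They assume that she completes the extension, receives every dose, and that each test result would be available before that day's injection. A woman already amenorrheic for 52 weeks at Day 0 is in the first row on either reading of the timing phrase. Every case in which 12 months is reached after Day 0 depends on the wider reading.

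For a woman who does not enter the extension, the last dose is injection 6 at Week 20. If the first waived test is Week 12, she loses 2 tests and the dose count is 6 − 4 + 1 = 3. If it is Week 24, she loses 1 test and the count is 0.

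**3. Whether FSH is available.** Section 7.4.2 schedules FSH at screening and at Weeks 4, 12, 24, 48, 72 and 96. It is therefore drawn at all 5 post-screening pregnancy-test visits.

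**The case against.** The strongest reply is that eligibility already does most of the work. Section 1.1 describes the disease at large and partly attributes hypogonadism to compression by a large adenoma. Exclusion 1 removes patients who need surgery for compression signs or symptoms, and exclusion 32 removes confirmed untreated hypogonadism. Prolactin adds less than it seems to: only "Prolactin (PRL) levels > 100 ng/mL" is excluded, but amenorrhea driven by lower prolactin values is still hypogonadism and still falls under exclusion 32 once confirmed. The waiver also only lifts a requirement, so a physician may go on testing. All of this stands, and it makes the group small. It does not close the gap for women on replacement or for those not confirmed at screening.

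Amenorrhea that begins on treatment fits the feared sequence less well. Such a woman is non-menopausal at onset, and her menstrual symptoms are reviewed at Main Phase visits and every 12 weeks in the extension. The later rows of the table therefore carry less weight than the first.

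Three stronger readings are tempting but not supported:

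- **Contraception is waived as well.** The protocol does not define childbearing potential, so a site might borrow the wording of 7.5.6.7. The text does not say so, and it releases no one from exclusion 25 or section 11.4.
- **Every injection after the last required test is due to the waiver.** A woman tested only at screening could receive all 24. However, injections 1 to 3 precede the Week 12 test for everyone, and a fully tested woman is also dosed between tests.
- **Most women in the trial are exposed.** The general statement about hypogonadism precedes the exclusions and cannot be applied to the enrolled group.

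**Conclusion.** The point holds as a minor participant-safety flaw. As written, the 12-month route can classify tumor-related amenorrhea as menopause and end required testing. At most 5 post-screening tests are lost and at most 21 doses are affected, for a woman who qualifies by Week 12 and completes the extension. The dose figure falls to 18, 12, 6 and 0 for later first waived tests. These figures rest on a 52-week year, full dosing and same-day results. Cases qualifying on study rest also on an ambiguous timing phrase. The number of women concerned cannot be derived. Contraception remains the main safeguard and testing is the back-up. Nothing in the efficacy analysis changes.

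**What to change.** Reword the 12-month route in 7.5.6.7 along these lines: *12 months of spontaneous amenorrhea with physiological menopause, supported by age and clinical history or by FSH > 40 mIU/mL on a scheduled sample. Amenorrhea attributable to the adenoma, or treated as hypogonadism under exclusion 32, does not qualify. Scheduled serum tests restart if bleeding returns.* The same edit should say whether the timing phrase applies to both routes.

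The FSH threshold is the one the section already uses, and no new sample is needed. The cost is at most 5 serum tests per woman who would otherwise be exempt, at visits where blood is already drawn. Some truly post-menopausal women, such as those on replacement with suppressed FSH, will be tested unnecessarily. FSH is also imperfect because Table 1-1 lists adenomas that secrete it, so age and history are offered as the alternative support. That leaves some clinical judgement, since the documents supply no age cut-off. SAP Table 2 reports childbearing status once, as a demographic, and cannot follow a change in status. If exemption and restart are to be documented, a small record elsewhere may be needed.
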